#### 5.7.1.1. Parameters

Immunogenicity assessments may include, but are not limited to, the humoral and cellular immunogenicity assays (as available and applicable) summarized in [Table 3](#).

**Table 3: Summary of Immunogenicity Assays**

Endpoint	Assay
Secondary endpoints	
Quantification of antibody binding to HA stem or full-length HA	ELISA
Exploratory endpoints	
Neutralization	Virus neutralization assay
Fc-mediated functionality	Human Fc Y RIIIa reporter assay
Breadth of the antibody response within Group 1 or beyond	ELISA using full-length HAs indicative of clade or group coverage
HA stem- or epitope-specificity	ELISAs using HA stem protein or competition ELISAs using bnAbs or HA proteins
Functional breadth of the antibody response within Group 1 or beyond	Virus neutralization assays or serum transfer into animal challenge models
Functional characterization of the antibody response	Assays assessing Fc-mediated functions (eg, antibody-dependent cytotoxicity assay, or antibody-dependent cellular phagocytosis assay), HA conformational change assays, or other assays
Molecular characterization of the antibody response	Assays assessing the epitope-specificity, glycosylation status, or other characteristics of the antibody (eg, systems serology arrays)
Innate immune responses	Transcript- or cytokine profiling
Gene expression profiles	RNA sequencing or other transcriptional profiling methods, including, but not limited to TCR or BCR repertoire analysis
Nasal antibody response	IgA and/or IgG ELISA in nasal secretions
Hemagglutination inhibition	HAI assays

BCR = B cell receptor; bnAbs = broadly neutralizing antibodies; ELISA = enzyme-linked immunosorbent assay; Fc = fragment crystallizable; HA = hemagglutinin; HAI = hemagglutination inhibition; Ig = immunoglobulin; RNA = ribonucleic acid; TCR = T cell receptor.

**Table 4** Presents the core assay package for this study.

**Table 4: Core assay package for VAC21148FLZ1001**

Parameter	Assay	Antigen
Stem-binding Ab (core assays)	H5 IgG ELISA and using trimeric full-length HA of a heterosubtypic Group 1 strain	H5 A/Vietnam/1203/2004 monobasic cleavage site, uncleaved (UFV190837)
	Mini-HA ELISA	Mini-HA protein with H1 A/Cal/09 backbone
Functionality	Neutralization by H5 Plaque Reduction Neutralization Test (PRNT) Influenza-virus HA matching core ELISA	H5N1 NIBRG-14 reassortant of A/Vietnam/1194/2004(H5N1) and A/PR/8/34(H5N1), polybasic cleavage site excised
	Fc-mediated effector function by H5 Human Fc γ RIIIa reporter assay (Promega) HA matching core ELISA	H5 A/Vietnam/1203/2004, monobasic cleavage site, uncleaved, membrane bound (UFV191437)
Breadth panel	IgG ELISAs using additional trimeric full-length HAs antigens	See breadth-panel Table 5
Locality	IgA and/or IgG ELISA in nasal secretions	H5 A/Vietnam/1203/2004 monobasic cleavage site, uncleaved (UFV190837)
Durability	H5 IgG ELISA and using trimeric full-length HA of a heterosubtypic Group 1 strain	H5 A/Vietnam/1203/2004 monobasic cleavage site, uncleaved (UFV190837)

### 5.7.1.2. Handling of Missing and/or Unquantifiable Immune Response Data

Missing immune response data will not be imputed.

Values below the lower limit of quantification (LLOQ) will be imputed based on the type of analysis:

- For the calculation of the geometric mean titer, values below LLOQ will be imputed to LLOQ/2.
- For the calculation of the geometric mean of the increase from baseline and calculation of the Breadth Coverage, values below LLOQ will be imputed to LLOQ.

Data above the upper limit of quantification (ULOQ) will be imputed with the ULOQ.

The LLOQ or limit of detection [LOD], as applicable, and ULOQ values per assay are available in the database.

### 5.7.1.3. Handling of Changes in Assay Status throughout the Study Conduct

In case of changes in assay status, for example in case the assay range is extended or when going from “qualified” to “validated”, the LLOQ and ULOQ are likely to change as well. Should this happen, then the SDTM database will contain records pertaining to the assay in the qualified status and records pertaining to the validated status, and the LLOQ and ULOQ values will also differ.

### 5.7.1.4. Immune Response Analysis

No formal hypothesis on immunogenicity will be tested.

### 5.7.1.5. Immunogenicity

#### 5.7.1.5.1. Humoral assays

For ELISAs (H5-ELISA and mini-HA ELISA) and VNA the following results will be calculated: N, geometric mean§ and corresponding 95% CI of the actual values, and fold increases from baseline will be tabulated and graphically presented. *§calculate the mean and corresponding 95% CI of log10 transformed values, back-transform this mean [i.e., 10mean] and CI [i.e., 10CI].*

A sample is considered positive if the value is above the assay LLOQ.

A response will be defined as:

- if sample interpretation is negative at baseline and there is >4-fold increase from LLOQ (on the original scale), or,
- if sample interpretation is positive at baseline and there is a >4-fold increase from baseline (on the original scale).

Tables will show the sample positivity, responders, and the percentage of participants with a >2-fold increase.

Geometric mean ratios (GMR) § between active groups and placebo group (pooled across cohort 1 and 2), with corresponding 95% CIs will be estimated via an analysis of variance (ANOVA), using log-transformed post-baseline value as dependent variable and study group as independent variable. As a sensitivity analysis, the ANOVA may also be performed adjusting for the respective baseline titers, by including log-transformed baseline titer as additional covariate. *§by back-transform LSmean and corresponding 95% CI from ANOVA [i.e., 10LSmean] and CI [i.e., 10CI].*

Actual values and fold changes from baseline are tabulated and shown as dot plots with dots for participant values, and the corresponding geometric mean and 95% CI per time point for each assay.

In the graphs, original values will be displayed on the log10 scale. The actual values will be shown, even if they are below the LLOQ. The LLOQ cut-off will be visualized in the graph per assay. Participant profiles of the actual values over time will also be graphically presented. A correlation plot of H5 ELISA versus mini-HA ELISA will be provided for the most important time points (at minimum, Baseline, Day 29, and fold increase from Baseline at Day 29).

A correlation plot with the H5-ELISA versus. VNA, H5-ELISA vs. Human FcγRIIIa reporter assay, VNA vs. Human FcγRIIIa reporter, H5-ELISA vs. IgA and/or IgG ELISA in nasal secretions will be provided for the most important time points (at minimum, Baseline, Day 29 and fold increase from Baseline at Day 29). In these scatterplots the actual values will be shown, even if they are below the LLOQ. The LLOQ cut-off will be visualized in the graph per assay.

Additional graphs might be considered based on the review of the first data results, potentially assessing the role of pre-existing immunity on the vaccine induced immune response.

Additional graphs might be considered for participants who developed ILI symptoms or have RT-PCR influenza infection.

**Human FcγRIIIa reporter assay** data will be presented in a similar way to core assays as described above.

**Breadth of the antibody response** within Group 1 will be assessed by IgG ELISAs using additional trimeric full-length HA breadth panel as presented in **Table 5** below:

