9.2. Sample Size Determination

The study will evaluate whether INFLUENZA G1 mHA, with or without Al(OH)₃ adjuvant, is safe, well tolerated and immunogenic in healthy adults aged ≥ 18 to ≤ 45 years.

There are 170 participants planned to be randomized in this study.

With 25 participants in one vaccine regimen, the observation of no vaccine reactions after the first vaccination would be associated with a 95% confidence that the true rate is less than 11.3%. Across active regimens (N=150), the observation of 0 vaccine reactions after the first vaccination would be associated with a 95% confidence that the true rate is less than 2.0%.

[Table 4](#) below shows the probabilities of observing at least one AE in samples of different sizes at given true AE rates. Placebo recipients will be shown pooled.

Table 4: Probability of Observing at Least One Adverse Event at a Given True Adverse Event Rate

True Adverse Event Rate	Probability of Observing at Least One Adverse Event in N Participants		
	N=25	N=50	N=150
0.5%	12%	22%	53%
1%	22%	39%	78%
2%	40%	64%	95%
5%	72%	92%	100%
10%	93%	99%	100%
25%	100%	100%	100%

N = number of participants

This is the first study in humans and standard deviation of selected immunological assays is not yet known in this population. Immunogenicity will be based on the estimation of geometric mean titer (GMT) ratios at each timepoint versus baseline and their corresponding 95% confidence intervals (CIs).

Assuming that approximately 12% of participants might be excluded from Per-protocol Immunogenicity (PPI) due to dropout or major protocol deviation impacting immunogenicity, we will have 22 participants per regimen. [Table 5](#) below presents the power of the study to detect a significant difference for several true ratios, assuming a range of standard deviations for ELISA on the log10 scale (two-sided alpha = 0.05).

Table 5: Power to Detect a Significant Difference at a Given True Ratio

Fold Change (Difference on Log10 Scale)	Assumed Standard Deviation on Log10 Scale					
	0.181	0.301	0.421	0.542	0.643	0.783
1 (diff. on log10=0) - no difference	5.0%	5.0%	5.0%	5.0%	5.0%	5.0%
1.5 (diff. on log10=0.176)	88.5%	47.4%	27.3%	18.4%	14.4%	11.3%
2 (diff. on log10=0.301)	100.0%	90.0%	63.9%	43.7%	32.9%	23.8%
3 (diff. on log10=0.477)	100.0%	100.0%	95.6%	81.4%	67.2%	50.6%

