### 5.7.1.6.2. Humoral assays

Descriptive statistics and graphs on humoral immunogenicity data listed in [Table 4](#) (where available) will be done similarly as described in section [5.7.1.5.1.](#) for the COV3005 Broad SF-SC cohort (H5 ELISA, mini-HA ELISA, VNA, Human Fc $\gamma$ RIIIa reporter assay, breadth ELISAs including three breadth scores, coverage score, and HAI assay) and for the SF-SC cohort.

For H5 ELISA, mini-HA ELISA, VNA, Human Fc $\gamma$ RIIIa reporter assay, and three breadth scores, geometric mean ratios (GMR)  $\ddagger$  between active groups (FLZ1001 vs. SF-SC cohort), with corresponding 95% CIs will be estimated via an analysis of variance (ANOVA), using log-transformed 28 days post-dose 1 immune parameter response as dependent variable and study group as independent variable. As a sensitivity analysis, the ANOVA may also be performed adjusting for the respective baseline titers, by including log-transformed baseline titer as an additional covariate.  $\ddagger$ by back-transform LSmean and corresponding 95%CI from ANOVA [i.e.,  $10^{LSmean}$ ] and CI [i.e.,  $10^{CI}$ ].

In addition, GMR plots over time, combining the regimens in one graph (without individual participant dots) will also be created.

For the breadth coverage, least square mean differences between active groups (FLZ1001 vs. SF-SC cohort), with corresponding 95% CIs will be estimated via an analysis of variance (ANOVA), using 28 days post-dose 1 breadth coverage as dependent variable and study group as independent variable. As a sensitivity analysis, the ANOVA may also be performed adjusting for the respective baseline value, by including baseline breadth coverage as an additional covariate.

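### The GMR and breadth-coverage intervals assume one residual variance across groups, so if spread differs their nominal 95% coverage can miss in either direction

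*SAP*

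**What the plan says.** SAP 5.7.1.5.1 estimates GMRs "between active groups and placebo group (pooled across cohort 1 and 2") by an ANOVA "using log-transformed post-baseline value as dependent variable and study group as independent variable". The intervals are obtained "by back-transform LSmean and corresponding 95% CI from ANOVA". The section names no group-specific variance, Welch interval, robust standard error or check of equal variance. The one sensitivity analysis is optional and concerns something else: "the ANOVA may also be performed adjusting for the respective baseline titers".

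The same model serves the breadth scores and, on the untransformed scale, the breadth-coverage AUC. SAP 5.7.1.6.2 uses it for FLZ1001 against SF-SC, with "28 days post-dose 1 immune parameter response as dependent variable and study group as independent variable". The SAP does not say whether all groups enter one model.

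On spread, Protocol 9.2 states: "This is the first study in humans and standard deviation of selected immunological assays is not yet known in this population". Its Table 5 is built "assuming a range of standard deviations for ELISA on the log10 scale (two-sided alpha = 0.05"). No SD is given for any regimen, placebo or SF-SC. Both documents say that no immunogenicity hypothesis is tested. Protocol 9.5 and SAP 5.8 say that safety and immunogenicity results inform which regimen goes forward.

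**The concern.** An ordinary one-way ANOVA estimates a single residual variance from all groups and uses it in every contrast. The groups here differ in dose level, adjuvant, number of active doses and, for placebo, in having no vaccine response at all. SAP 5.7.1.2 also sets values below LLOQ to LLOQ/2 for geometric means and caps values at ULOQ, which compresses spread in any group that sits near a limit. Equal variance is therefore an assumption that may fail, and the plan has nothing in place if it does.

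At stake is whether an interval labelled 95% behaves like one. In a descriptive study the interval carries the uncertainty statement, and these contrasts are among the results that the sponsor's committee will see when it chooses a regimen.

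**Working it through.** **Inputs.** Protocol 9.2 allows for 12% exclusion: 25 × 0.88 = 22, hence "we will have 22 participants per regimen". Placebo is 170 − 150 = 20 randomised. Applying the same 12% gives 17.6, taken as 18 (an assumption). SDs are drawn from Table 5's list (0.181 to 0.783 log10). Which group has which SD is also an assumption.

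**The plan's own figure.** Table 5 is a two-sample t-test with a common SD, 22 per group and 42 df. For a 2-fold difference at SD 0.301 the noncentrality is 0.301 / (0.301 × √(2/22)) = 3.32, and the power is 90.0%, as printed. All 18 cells with a real difference reproduce within 0.2 points. Table 5 therefore shows alternative values of one common SD. The documents print no coverage figure for the GMR intervals.

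**Formulas.** With six regimens of 22 and placebo of 18, residual df = 6 × 21 + 17 = 143 and t = 1.977.

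- ANOVA SE = √[MSE × (1/22 + 1/18)], where MSE = Σ(n−1)s² / 143
- True SE = √(s_k²/22 + s_p²/18)
- The interval is too narrow when ANOVA SE / true SE is below 1, and too wide when it is above 1.

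**Worked case.** One regimen has SD 0.643 and all other groups 0.301.

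- MSE = (21 × 0.643² + 122 × 0.301²) / 143 = 0.138, root 0.372
- ANOVA SE = 0.372 × 0.318 = 0.118
- True SE for the variable regimen = √(0.413/22 + 0.0906/18) = 0.154, ratio 0.77
- True SE for the other regimens = 0.0957, ratio 1.23

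**Coverage of nominal 95% intervals** (40,000 simulated trials per pattern; where two values are given, the more variable regimen comes first, then the others):

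| SD pattern (log10) | Root MSE | SE ratio | ANOVA | Welch |
|---|---|---|---|---|
| All groups 0.421 | 0.421 | 1.00 | 95% | 95% |
| One regimen 0.542, rest 0.301 | 0.347 | 0.81 / 1.15 | 89.0% / 97.5% | 95% |
| One regimen 0.643, rest 0.301 | 0.372 | 0.77 / 1.23 | 86.3-86.7% / 98.3% | 95% |
| Two regimens 0.643, rest 0.301 | 0.431 | 0.89 / 1.43 | 91.6-91.8% / 99.4% | 95% |
| Placebo 0.542, all active 0.301 | 0.339 | 0.75 | 86% | 95% |
| All active 0.542, placebo 0.301 | 0.519 | 1.22 | 98% | 95% |
| One regimen 0.643, five 0.542, placebo 0.301 | 0.536 | 1.10 / 1.26 | 97.1% / 98.6% | 95% |

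In the third row the median 95% interval for the variable regimen is ×/÷1.71 from the ANOVA and ×/÷2.05 from Welch. For the other regimens it is ×/÷1.71 and ×/÷1.56.

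**Separate two-group models.** If each active-placebo contrast were its own ANOVA, coverage would be 93-96% in these patterns.

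**SF-SC.** Take n = 76, the number that the SAP names for the extended breadth subset, and leave placebo out of the model (both assumptions). Then df = 126 + 75 = 201.

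- SF-SC 0.542, all active 0.301: ANOVA SE 0.0988, true SE 0.0894, ratio 1.11, coverage 97%.
- All active 0.542, SF-SC 0.301: ANOVA SE 0.1130, true SE 0.1206, ratio 0.94, coverage 93%.
- One regimen 0.542, all else 0.301: MSE = (21 × 0.294 + 180 × 0.0906) / 201 = 0.112, ANOVA SE = √(0.112 × (1/22 + 1/76)) = 0.081, true SE 0.1206, ratio 0.67, coverage about 81%.

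So the error is smaller than against placebo when the active groups share one SD. A large comparator does not protect a single more variable regimen. In that last pattern a separate two-group model does not rescue it either: pooled variance (21 × 0.294 + 75 × 0.0906) / 96 = 0.135, SE 0.089, ratio 0.74, coverage about 86%.

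**The case against.** The strongest reply is that the unfavourable cases are chosen. Table 5's range expresses ignorance about one SD and is no evidence that groups differ. Groups 4 and 6, and Groups 5 and 7, receive the same Day 1 vaccine and diverge only at Day 57, so at Day 29 a single outlying regimen could only be Group 1 or Group 2. If Groups 5 and 7 are the variable pair, coverage is about 92-93% at SD 0.542 or 0.643. If all three adjuvanted groups are, it is about 95%. If all four high-dose groups are, it is 96-97%. All of this stands. It limits how bad the undercoverage is likely to be at Day 29. It does not remove the error, because the less variable groups in these patterns then get intervals that are too wide.

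One model for all groups is also an inference. It is the natural reading, but the SAP does not write it, and separate models would largely cure the placebo contrasts.

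It is further fair to say that the results are descriptive, that each group's geometric mean has its own interval beside plots of individual values, and that regimen choice weighs other factors. Own-SD intervals for geometric means next to ANOVA-based ratios are conventional and are not a contradiction.

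A reader might infer a stronger rule: that the most variable regimen always gets too narrow an interval and the others too wide. The documents do not support it. Every contrast shares the comparator, so a low-spread placebo can make all intervals too wide, the most variable regimen's included (last row of the table), and a high-spread placebo can make all of them too narrow.

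**Conclusion.** The point holds as a conditional one of minor severity. The planned model, read in the standard way, has no protection against unequal spread, and the error can go either way. Against placebo, the illustrated coverage runs from about 86% to above 99%, while Welch intervals stay at about 95% throughout. These sizes rest on three assumptions: SD patterns that the documents do not supply, 18 placebo participants in the per-protocol set, and one model for all groups. Nothing in the documents shows that any particular regimen will be reported with false precision, and no formal test is affected.

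**What to change.** In SAP 5.7.1.5.1 and 5.7.1.6.2, fit the same models with group-specific residual variances and Satterthwaite (Welch-type) degrees of freedom. Apply this to the unadjusted and baseline-adjusted versions, and to the titre GMRs, breadth scores and breadth coverage. Add a phrase saying which groups enter each model. If some outputs already exist under the planned model, show the unequal-variance intervals beside them.

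The cost is one model option and one or two sentences, with no extra data. If the variances are in fact equal, intervals widen slightly: a median factor of about 1.86 instead of 1.84 at SD 0.421.

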Blood and urine samples for clinical laboratory assessments will be collected as indicated in Section 1.3 Schedule of Activities and Section 10.6, Appendix 6: Clinical Laboratory Tests.

Blood will be collected from all participants to assess humoral immune responses pre-vaccination on each dosing day, at 7 days and at 28 days after each dose, at 6 months after the second dose, and at 12 months after the first dose (or at the early exit visit if the participant prematurely terminates the study without withdrawing consent ^a).

Participants should record signs and symptoms of influenza during the influenza season using a specific Influenza Intensity and Impact Questionnaire (Flu-iiQTM) and an ILI form. Participants will be informed of the timing of the start and end of the influenza season in accordance with the country/region-specific influenza local surveillance system. Procedures for Flu-iiQTM questionnaire and ILI form completion are described in Section 8.1.1, ILI Procedures. The Flu-iiQTM questionnaire and ILI form will be the primary source for influenza monitoring. Participants will be contacted by telephone or other means of communication every 14±3 days (unless a planned clinic visit has occurred or will occur within 14 days). Calls will remind the participants to complete the Flu-iiQTM questionnaire and ILI form in the event of any symptoms of influenza infection, to contact the site at the time of symptom onset, and to take a nasal swab at home preferably on the day of symptom onset or the day thereafter (ILI Days 1-2). Calls will also check for any SAEs and associated concomitant medications since the previous visit or telephone contact.

Full details of ILI procedures, including the collection of nasal swabs are provided in Section 8.1.1, ILI Procedures.

The presence of influenza virus infection will be assessed by qualified site staff by RT-PCR diagnostics and/or rapid-PCR detection (eg, by Cepheid GeneXpert[®]) on the nasal swab samples.

Seasonal Influenza Vaccination

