8.1. Immunogenicity Assessments

Immunogenicity assessments may include, but are not limited to, the immunogenicity assays (as available and applicable) summarized in [Table 3](#). Timings of blood draws are specified in Section [1.3](#), Schedule of Activities.

Immunogenicity assessments supporting the secondary endpoint were chosen to quantify the magnitude of the pre-existing influenza-specific immunity and vaccine-induced antibody responses that are thought to contribute to the protective capacity of HA stem-based vaccination approaches. Antibodies targeting the stem domain of the influenza HA molecule will be quantified by ELISA using full-length HA or stem-only antigens that are expected to sensitively and specifically detect responses targeting the conserved stem domain of the molecule.

Immunogenicity assessments supporting the exploratory endpoint were chosen to further quantify the magnitude and characterize pre-existing influenza-specific immunity and vaccine-induced immune responses. This characterization entails a deeper investigation of the breadth and functionality of the antibody response, the set-up of assays and characterization of mucosal targeting of the immune response, and characterization of cellular and molecular effects of vaccination.

Although this study is not designed to support the identification or validation of surrogates of protection against clinically manifest influenza infection, immunological assessments supporting the secondary and exploratory endpoints will be evaluated for their utility as potential surrogates of protection, to be applied to and further characterized in follow-up studies, such as challenge studies or Phase 2b proof-of-concept studies.

Blood for humoral immune responses will be drawn from all participants. Influenza immunity in study participants will be determined on baseline (Day 1) and post-vaccination blood samples as described in Section [1.3](#), Schedule of Activities. Both assay variability and pre-existing immunity will be taken into consideration in the immunogenicity assessments.

PaxGene tubes and proteome stabilization samples will be collected according to Section [1.3](#), Schedule of Activities. PaxGene samples will allow the performance of whole blood transcript profiling.

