Geometric mean ratios (GMR)§ between active groups and placebo group (pooled across cohort 1 and 2), with corresponding 95% CIs will be estimated via an analysis of variance (ANOVA), using log-transformed post-baseline value as a dependent variable and study group as independent variable. As a sensitivity analysis, the ANOVA may also be performed adjusting for the respective baseline value, by including log-transformed baseline value as an additional covariate. §by back-transform LSmean and corresponding 95%CI from ANOVA [i.e.,  $10^{\text{LSmean}}$ ] and CI [i.e.,  $10^{\text{CI}}$ ].

Fold changes from baseline will be shown as dot plots with dots for participant values, and the corresponding geometric mean and 95% CI per time point for each assay.

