For the Breadth coverage AUC, the following results will be calculated: N, mean and corresponding 95% CI, interquartile range, min, max of the actual values, and mean increases from baseline will be tabulated and graphically presented. Reverse cumulative breadth coverage plots for each group will be presented based on individual breadth coverage. Least square means between active groups and the placebo group (pooled across cohort 1 and 2), with corresponding 95% CIs will be estimated via an analysis of variance (ANOVA), using post-baseline value as a dependent variable and study group as independent variable. As a sensitivity analysis, the ANOVA may also be performed adjusting for the respective baseline value, by including baseline value as an additional covariate.

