### **5.7.1.6. External control group from VAC31518COV3005 study**

VAC31518COV3005 (COV3005) is a randomized, double-blind, phase 3 study to evaluate safety, reactogenicity, and immunogenicity of co-administration of Ad26.COV2.S and influenza vaccines in healthy adults 18 years of age and older. The study aims to assess the safety, reactogenicity, and immunogenicity of the Ad26.COV2.S vaccine co-administered with a quadrivalent standard-dose or high-dose seasonal influenza vaccine compared to administration of each vaccine separately to explore whether Ad26.COV2.S and the influenza vaccines can be administered concomitantly.

Without a seasonal flu vaccinated control group in FLZ1001, samples from COV3005 participants will be used to assess the performance of FLZ1001 assays and stem binding response upon seasonal influenza vaccination. Samples from COV3005 participants will be used as an external control group and referred to as a Seasonal Flu vaccinated reference Serum Collection (“SF-SC”). Those samples will run alongside FLZ1001 study samples in all assays. The COV3005 study includes the same target population as the FLZ1001 study, healthy adults aged  $\geq 18$  to  $\leq 45$  years, and also includes older adults, the main envisioned target population of the Uniflu vaccine.

Details on the purpose and random selection of samples are presented in Universal Influenza Vaccine Study plan in COV3005 (TV-REF-281637).

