#### **5.7.1.6.1. Populations (analysis sets) for COV3005 analysis**

**Broad SF-SC:** At the first stage, 200 subjects who received the standard dose seasonal flu vaccination and did not receive Ad26.COV2.S vaccination (Broad SF-SC) were randomly selected to assess the performance of FLZ1001 assays on seasonal flu-vaccinated subjects (stratified by age group).

**SF-SC:** At the second stage, out of those 200 subjects a subset (SF-SC) will be selected to match as much as possible the population enrolled in FLZ1001. A direct comparison of FLZ1001 immunogenicity data will be made to the SF-SC cohort.

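### Baseline adjustment of the between-group immunogenicity estimates is only optional, which costs precision against placebo and leaves any residual baseline gap in the SF-SC ratio

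*SAP*

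**What the plan says.** SAP 5.7.1.5.1 estimates titre GMRs of each active group against pooled placebo from an ANOVA on the log post-baseline value with study group as the only factor. It then adds: "As a sensitivity analysis, the ANOVA may also be performed adjusting for the respective baseline titers, by including log-transformed baseline titer as additional covariate".

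The same structure appears in three other places:
- Breadth Score (SAP 5.7.1.5.1): "the ANOVA may also be performed adjusting for the respective baseline value", again as an optional sensitivity analysis.
- Breadth Coverage (SAP 5.7.1.5.1): the model is fitted "using post-baseline value as a dependent variable and study group as independent variable", with adjustment optional.
- FLZ1001 against the external seasonal-vaccine cohort SF-SC (SAP 5.7.1.6.2): the model is fitted "using log-transformed 28 days post-dose 1 immune parameter response as dependent variable and study group as independent variable", with adjustment optional.

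SF-SC is drawn from another trial and "will be selected to match as much as possible the population enrolled in FLZ1001" (SAP 5.7.1.6.1). The matching variables are not listed; SAP 5.7.1.6 points elsewhere: "Details on the purpose and random selection of samples are presented in Universal Influenza Vaccine Study plan in COV3005".

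On baseline, Protocol 4.1 states: "Blood will be collected from all participants to assess humoral immune responses pre-vaccination on each dosing day". Protocol 8.1 promises: "Both assay variability and pre-existing immunity will be taken into consideration in the immunogenicity assessments". Within-group fold rises, a responder definition relative to baseline and baseline geometric means are all committed. Graphs exploring pre-existing immunity are optional.

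**The concern.** The baseline value is planned for everyone and the protocol says it will count, yet no committed between-group estimate uses it.

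Against placebo this is a matter of precision. No model compares active regimens directly, so a model-based comparison of two regimens has to go through their two placebo GMRs, and the loss carries into that ratio. Immunogenicity is one of several inputs to the choice of regimen (Protocol 9.5, SAP 5.8).

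Against SF-SC it is a matter of bias. Nothing is randomised between the two studies. If baseline titres still differ after matching, part of that difference is carried into the Day 29 GMR, and its 95% CI makes no allowance for it. Tabulated baselines would reveal the gap without correcting the ratio.

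Leaving the adjusted model optional also means that whether it is run and reported can be decided after results are seen.

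**Working it through.** **Inputs from the documents.** There are 22 evaluable participants per regimen, 25 × 0.88 (Protocol 9.2). Pooled placebo is 20, and 20 × 0.88 = 17.6, taken as 18. SDs come from the log10 grid in Protocol Table 5. SF-SC is taken as 76, the number given for the extended breadth panel; using it for the whole cohort is an assumption.

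**Assumed.** Baseline-to-post correlation rho, within-group log-log slope b, baseline GMT ratio B and baseline assay reliability.

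**Reproducing the plan.** A two-sample t-test, 22 versus 22, two-sided 0.05, 2-fold difference, gives power of 90.0%, 63.9% and 43.7% at SD 0.301, 0.421 and 0.542. These match Table 5.

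**Placebo contrast.** The CI factor is 10^(t × SD × √(1−rho²) × √(1/n1+1/n2)). Six active groups of 22 plus 18 placebo make 150, so df = 143, or 142 with the covariate. At SD 0.421 the unadjusted exponent is 1.977 × 0.421 × √(1/22+1/18) = 1.977 × 0.1338 = 0.2645, and 10^0.2645 = 1.84.

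| Contrast | SD | Unadjusted | rho 0.3 | rho 0.5 | rho 0.7 |
|---|---|---|---|---|---|
| 22 v 18 | 0.301 | 1.55 | 1.51 | 1.46 | 1.36 |
| 22 v 18 | 0.421 | 1.84 | 1.79 | 1.69 | 1.54 |
| 22 v 18 | 0.542 | 2.19 | 2.11 | 1.97 | 1.75 |
| 22 v 22 (ratio of two regimen GMRs) | 0.421 | 1.78 | 1.74 | 1.65 | 1.51 |

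On the log scale the interval narrows by 4.6%, 13.4% and 28.6%. At rho 0 there is no gain.

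**SF-SC, unadjusted.** The GMR is multiplied by B^b. Coverage follows from the non-central t with df 96 and non-centrality b × log10(B) / (0.421 × √(1/22+1/76)), whose denominator is 0.1019. For B = 1.5 and b = 0.5: 0.5 × 0.1761 / 0.1019 = 0.864, which gives 86.3%.

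| B | b | GMR off by | Coverage |
|---|---|---|---|
| 1.2 | 0.3 / 0.5 / 0.7 | 1.06 / 1.10 / 1.14 | 94.4 / 93.3 / 91.6% |
| 1.5 | 0.3 / 0.5 / 0.7 | 1.13 / 1.22 / 1.33 | 91.9 / 86.3 / 77.6% |

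At B = 1 there is no bias. At B = 1.5 coverage depends strongly on SD: 78 / 49 / 21% at SD 0.181 and 94 / 93 / 90% at SD 0.783.

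**Ratio of fold rises instead.** Its bias is B^(b−1). At B = 1.5 this is 0.75 / 0.82 / 0.89, in the opposite direction. With equal baseline and post SDs, coverage is 83 / 86 / 90%.

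**How well adjustment works for SF-SC (simulation, SD 0.421).**
- Common slope and no baseline assay error: about 95% coverage.
- Baseline assay error, B = 1.5, observed slope 0.7: the true slope is 0.7/reliability and the remaining bias is B^(true − observed slope). At reliability 0.8 this is 1.5^(0.875−0.7) = 1.07, coverage 93%. At 0.7 it is 1.5^(1.0−0.7) = 1.13, coverage 89%. Unadjusted, the figures are 1.43 with 68% and 1.50 with 60%.
- Unequal slopes, 0.3 in FLZ1001 and 0.7 in SF-SC, target the GMR at the overall mean baseline:

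| Model | B = 1.0 | B = 1.2 | B = 1.5 |
|---|---|---|---|
| Unadjusted | 95% | 94% | 90% |
| Common slope | 90% | 90% | 88% |
| Separate slopes, HC3 | 95% | 95% | 94% |

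With equal slopes of 0.5 and no gap, the separate-slope CI factor is 1.53 against 1.50 for the common slope.

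**The case against.** The analysis is descriptive: no immunogenicity hypothesis is tested, and Protocol 9.2 bases immunogenicity on ratios to baseline. The SAP already commits to fold rises, baseline-conditional responders and participant profiles, so the Protocol 8.1 promise is partly met. That is fair, but none of these puts baseline into a between-group estimate.

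Against placebo the unadjusted ANOVA is valid, and the gains above assume one common correlation. Unvaccinated repeat samples may correlate more closely than vaccinated ones. With slopes of 0.3 in active and 0.9 in placebo groups, the common-slope model only narrows the factor from 1.84 to 1.76, with 97% coverage; separate slopes with HC3 give 1.57 and 94%. This stands. The placebo part is a modest precision point of uncertain size.

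For SF-SC, baseline titre may already be a matching variable in the plan not seen here, and SAP 5.8 words the external-control analyses as possible, not certain. A plain covariate can also do worse than no adjustment when slopes differ. The first two points make the bias conditional. The third is why a covariate alone is not enough there.

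Finally, the unadjusted GMR does correctly estimate the ratio of observed GMTs. It is biased only as an estimate of the vaccine contrast at equal baseline. In a direct comparison with a cohort chosen to resemble the trial population, the contrast at equal baseline is the natural reading.

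**Conclusion.** The concern holds. No between-group estimate that uses baseline is guaranteed anywhere in the SAP. Against placebo the consequence is lost precision only: 5% to 29% on the log scale for correlations of 0.3 to 0.7, and nothing at zero. Against SF-SC the consequence is bias if a baseline gap survives matching: none at equal baselines, slight at 1.2-fold, and up to 1.33 with 78% coverage at 1.5-fold and SD 0.421.

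These sizes rest on assumed correlations, slopes, gaps and reliability, and on 76 SF-SC participants. The estimates and their intervals are affected; no type I error claim is made. This should be changed, with the SF-SC comparison the more important part.

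**What to change.** 1. Make the baseline-adjusted analysis mandatory in all four places and report it beside the unadjusted one. If the primary analysis has already been unblinded, report both and document the change in SAP Appendix 2. Make the adjusted model the main one only if it has not.
2. Use log10 baseline as covariate for titres and breadth scores. Use untransformed baseline AUC for breadth coverage, which is already built on log10(value/LLOQ) and can be zero.
3. State how baseline values below LLOQ enter the titre covariate. SAP 5.7.1.2 uses LLOQ/2 or LLOQ depending on the analysis and names neither for this model.
4. Show baseline GMTs next to the GMRs and report the group-by-baseline interaction.
5. For SF-SC, also report the separate-slope GMR at the overall mean baseline with HC3 standard errors, whatever the interaction shows, and name the matching variables in the SAP.

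The cost is low. The covariate model is already written as an option and needs no new data; the separate-slope model, the LLOQ rule and the matching list are small additions. Participants without a Day 1 value drop out of the adjusted model. Timing needs care: SAP version 2.0 is tied to the final-analysis lock, and its Extended Breadth Coverage text is in the past tense, so this may be a post-unblinding change. Adjustment will not remove baseline assay error or other differences between the two studies.
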